#### 10.2.5 Early Termination (ET) visit

Participants prematurely discontinued from the study would be encouraged to complete an ET visit within 30 days of last dose. The investigator should make every effort to perform following assessments at the early termination visit in case if any participant discontinues from

Approved by: [name] No.: SARO.20.001
[name]	Version No.: 4.0

#### CONFIDENTIAL Page 60 of 109

the study prior to completion of his/her study treatment period (i.e. termination prior to Week 24 visit):

- Complete physical examination
- Vital signs measurement.
- AE assessment.
- Concomitant medication review
- Monitoring of diet, exercise, avoidance of alcohol, and other hepatotoxic agents (Refer Appendix 8).
- Compliance review for study medication
- Weight, Hip and waist minimal circumference measurements
- Fasting Laboratory evaluations
- Serum pregnancy test for all female participants of child bearing potential.

#### 10.3 STANDARDIZED QUESTIONNAIRES

**Alcohol Use Disorders Identification Test** (AUDIT) is a 10-item questionnaire with a simple scoring scale. The purpose of the questionnaire is to ascertain whether there is significant alcohol consumption prior to enrollment or after randomization. (Appendix 5).

**36-Item Short Form Health Survey (SF-36)** is an easily administered questionnaire that will be used to patient-reported health-related quality of life. (Appendix 4).

#### 10.4 ADHERENCE TO PROTOCOL

The investigator and the site staff shall strictly adhere to the protocol and International Council for Harmonization (ICH) Good Clinical Practice (GCP) guidelines. All participants will be encouraged to strictly follow the instructions given to them as per this protocol. For any deviation or violation from protocol considered serious, the participant may be withdrawn from the study at the discretion of the sponsor or the investigator.

#### 10.5 DATA AND SAFETY MONITORING BOARD

External oversight for this trial will be provided by an unblinded DSMB. An unblinded DSMB may meet regularly as per the DSMB charter to review interim data. The primary responsibility of the DSMB is to protect the safety and welfare of the participants participating in this clinical trial and to ensure the integrity of the clinical trial.

Specifically, for this study, the DSMB will be responsible for:

• Examining accumulated safety data and compliance data in order to make recommendations concerning continuation, termination, or modification of the trial based on the safety of the interventions under study.

Approved by: [name] No.: SARO.20.001
[name]	Version No.: 4.0

#### CONFIDENTIAL Page 61 of 109

- Reviewing major trial design modifications proposed by Sponsor or the investigator(s) prior to implementation of those modifications.
- The DSMB may review the safety data at any time as warranted by emerging results. Based on review of the safety data, the DSMB can recommend continuation of the study unchanged, study interruption, study termination, modification of the trial, or alteration in the DSMB monitoring plan.

Further information regarding the DSMB review process will be provided in the DSMB charter.

#### 10.6 PROTOCOL DEVIATIONS

For the purposes of this study, no distinction will be made between protocol violation and deviation. Deviation may be categorized as minor protocol deviation or major protocol deviation. Classification of protocol deviations as major or minor will be assessed at the blinded data review meeting prior to database lock. Minor protocol deviation includes any deviation that do not necessarily influence the results/outcome of primary endpoints or participant safety. Minor protocol deviation does not require immediate notification to the IRB unless otherwise specified by IRB requirements. All minor protocol deviations will be noted in monitoring reports and discuss with investigator/site personal. Major protocol deviation includes any violation, which may influence the results/outcome of primary endpoints or participant safety. Major protocol deviation must be reported immediately to the IRB, as specified by the IRB requirements. All major protocol deviations will be reported to the sponsor immediately (Note: persistent non-compliance of minor protocol deviations may rise to the level of major protocol deviations). As a result of protocol deviations, corrective actions are to be developed and implemented promptly.

The sponsor reserves the right to terminate the study at a given center in the event of monitoring and/or auditing findings of serious or persistent non-compliance with the protocol, Standard Operating Procedures (SOPs), GCP, and/or applicable regulatory requirement(s) by an investigator/Institution. In all cases of site closure due to protocol deviations, the IRB and regulatory authority will be informed. The clinical study report (CSR) will provide a list of protocol deviations/violations in a separate section. The results will be analyzed for all participants regardless of protocol deviation occurrence.

Protocol deviations/violations will include but are not limited to the following:

- Violations of inclusion and exclusion criteria at randomization.
- Participants who met the withdrawal criteria but were not withdrawn.
- Participants who received the wrong treatment or incorrect dose.
- Participants who received an excluded medication.
- Serious non-compliance with regulatory or GCP guidelines.

Approved by: [name] No.: SARO.20.001
[name]	Version No.: 4.0

#### CONFIDENTIAL Page 62 of 109

#### 11. STATISTICAL CONSIDERATIONS

#### 11.1 GENERAL CONSIDERATIONS

A separate Statistical Analysis Plan (SAP) will be prepared and finalized before database lock. SAP will provide further details regarding the definition of analysis variables and analysis methodology to address all study objectives. The SAP will serve as a compliment to the protocol and supersedes it in case of differences.

The statistical evaluation will be performed using SAS® software version 9.4 or higher (SAS Institute, Cary, NC). All data will be listed and summary tables will be provided. Summary statistics will be presented by treatment group. Continuous variables will be summarized for the measured values and change from baseline values using the number of observations, mean, standard deviation, median, minimum, and maximum. Categorical variables will be summarized with counts and percent for each category.

#### 11.2 PARTICIPANT EVALUABILITY

Assignment to all analysis populations, including decisions made on inclusion/exclusion for the per-protocol population and other data handling issues will be agreed on and documented in a blinded data review meeting, to occur (with report finalized) prior to breaking the blinded treatment assignment code and locking the database. Protocol deviations and their impact on analysis populations will be listed for all randomized participants.

#### 11.3 ANALYSIS POPULATIONS

The following analysis populations are defined:

**All Enrolled Population**: includes all participants who signed an ICF. This analysis population will be used to summarize participant disposition and pre-treatment AEs.

**Safety Population**: includes all participants who received at least one dose of study drug (full or partial). Participants in the safety analysis population will be analyzed according to the treatment received. This analysis population will be used for all safety analyses.

**Intent-to-treat (ITT) Population**: includes all participants who are randomized and receive at least one dose of the study drug (full or partial). Participants in the ITT population will be analyzed according to the treatment group they are assigned at randomization. The ITT population will be the primary analysis population for all efficacy analyses.

**Per-Protocol (PP) Population**: includes all participants in the ITT population, received at least one dose of study drug, who are compliant with the study protocol with no major protocol deviations that are expected to affect the assessment of efficacy at Week 24/EOT.

Approved by: [name] No.: SARO.20.001
[name]	Version No.: 4.0

#### CONFIDENTIAL Page 63 of 109

Classification of protocol deviations as major or minor will be assessed at the Blinded Data Review Meeting prior to database lock.

#### 11.4 DEMOGRAPHIC AND BASELINE CHARACTERISTICS

Demographic and baseline characteristics will be summarized for ITT, PP and safety populations. All summaries will be presented by treatment group and overall.

The demographic parameters include age, gender, ethnicity and race. The baseline parameters include weight, BMI, fibrosis stage, ELF, FIB-4, APRI, NFS, PRO-C3 levels, liver stiffness, CAP, FAST score, liver parameters (ALT and AST), lipid profile parameters (Triglycerides, total cholesterol, HDL-C, LDL-C, small-dense LDL, non-HDL-C, VLDL-C), and comorbidities (Dyslipidemia, hypertension and type 2 diabetes).

#### 11.5 PRIMARY EFFICACY ANALYSIS

#### 11.5.1 Intercurrent Events

The following intercurrent events (ICEs) are envisioned during the study:

- Death
- Premature discontinuation of study treatment for reason other than AE, lack of efficacy (LoE), liver transplant, hepatic decompensation or bariatric intervention.
- Premature discontinuation of study treatment for reason of AE, lack of efficacy (LoE), liver transplant, hepatic decompensation or bariatric intervention.
- Receipt of prohibited medication at any point prior to Week 24 assessment.

#### 11.5.2 Estimands for the Primary Efficacy Endpoint

Primary and secondary estimands for the primary efficacy objective "To evaluate the effect of Saroglitazar Magnesium 4 mg compared with Placebo on changes in hepatic fat content measured by MRI MRI-PDFF at Week 24/EOT." are defined below:

#### 11.5.2.1 Definitions Applied to All Estimands

Criterion	Description
Treatment conditions of interest	Saroglitazar Magnesium 4 mg vs placebo
Population	Participants with NAFLD in PLWH

Approved by: [name] No.: SARO.20.001	
[name]	Version No.: 4.0	

#### CONFIDENTIAL Page 64 of 109

Criterion	Description	
Endpoint	Change from baseline in hepatic fat content at week 24/EOT	
Population level summary	Difference between treatments in change from baseline in hepatic fat content at week 24/EOT	

#### 11.5.2.2 Definitions Corresponding to Each Estimand

	Primary Estimand	Secondary Estimand	
ICEs and strategies to handle ICEs	Death prior to assessment at Week 24     Composite strategy     Premature discontinuation of study treatment for reason of AE, lack of efficacy (LoE), liver transplant, hepatic decompensation or bariatric intervention     Treatment policy strategy     Premature discontinuation of study treatment for reason other than AE, lack of efficacy (LoE), liver transplant, hepatic	Death prior to assessment at Week 24     Composite strategy     Premature discontinuation of study treatment for reason of AE, lack of efficacy (LoE), liver transplant, hepatic decompensation or bariatric intervention     Hypothetical strategy     Premature discontinuation of study treatment for reason other than AE, lack of efficacy (LoE), liver transplant, hepatic	
	decompensation or bariatric intervention  Treatment policy strategy	decompensation or bariatric intervention  Hypothetical strategy	
	Receipt of prohibited medication at any point up to Week 24  Treatment policy strategy	Receipt of prohibited medication at any point up to Week 24  Hypothetical strategy	
	ICE(s) with a composite variable strategy take priority over ICEs with other strategies.		

Where the strategies are described as follows in the sequence these strategies will be applied:

#### • For the primary estimand:

- Composite strategy: missing data will be handled by imputing using the worst outcome of MRI-PDFF across either treatment arm.
  - o Treatment policy strategy: available data occurring on or after the ICE will be analyzed as observed. Any missing Week 24 MRI-PDFF data due to discontinuation of study treatment for reason other than AE, lack of efficacy (LoE), liver transplant, hepatic decompensation or bariatric intervention will be multiple imputed using a missing at random (MAR) approach.
- For the secondary estimand:
- Composite variable strategy: missing data will be handled by imputing using the worst outcome of MRI PDFF across either treatment arm.

Approved by: [name] No.: SARO.20.001
[name]	Version No.: 4.0

#### CONFIDENTIAL Page 65 of 109

O Hypothetical strategy: the approach allows for the assessment of the treatment effect in an alternative, hypothetical setting where 1) all participants take the assigned study treatment without discontinuation/interruption, and 2) prohibited medication was not available to participants for the study duration. Available data occurring on or after the ICE will be set to missing, and multiple imputed by a MNAR application of SAS Proc MI based on the distribution of data for each treatment arm where all participants do not experience an ICE.

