#### 11.5.6 Handling of Missing Data

Every effort will be made to prevent participants early terminating the study and for participants who discontinue study drug, every effort will be made to continue to collect data after

Approved by: [name] No.: SARO.20.001
[name]	Version No.: 4.0

### CONFIDENTIAL Page 66 of 109

discontinuation. Where missing data exist for primary and secondary efficacy endpoints, imputation will occur where specified.

The primary method of imputation for missing data will be MI (Multiple Imputation); the MI procedure of the SAS system will be used to generate sets of data with missing values imputed from observed data. It is expected that the pattern of missing data will be monotonic, as the biopsy will be performed only at screening and at Week 24/EOT visits.

A logistic regression model will be used for the ordinal scores and linear regression will be used for the continuous variable.

The imputed datasets will be analyzed using the methodology described in Section 11.5. The results from the analysis of the multiple imputed datasets will be combined by the MIANALYZE procedure of the SAS system. The number of imputations and the seed to be used, plus any further details required, will be detailed in the SAP.

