#### 11.5.7 Sensitivity and Supportive Analyses

The following sensitivity and supportive measures will be conducted for the primary efficacy endpoint:

Estimand	Analysis Set	Modelling and Data Handling Method
Primary and secondary	PPS	Same as primary analysis method. Repeat on primary and secondary estimands with same imputation approach for missing data.

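### Does the primary-estimand imputation rule drop participants who stop for adverse events or lack of efficacy?

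*Protocol*

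**What the plan says.** Protocol Section 11.5.2.2 separates two kinds of treatment discontinuation. One is "Premature discontinuation of study treatment for reason of AE, lack of efficacy (LoE), liver transplant, hepatic decompensation or bariatric intervention"; the other is discontinuation for any other reason. Under the primary estimand both are handled by treatment policy. The text that follows says that "available data occurring on or after the ICE will be analyzed as observed". It then names MAR multiple imputation for one group: "Any missing Week 24 MRI-PDFF data due to discontinuation of study treatment for reason other than AE, lack of efficacy (LoE), liver transplant" (the list goes on to hepatic decompensation and bariatric intervention). Death is treated separately, with the worst outcome seen in either arm.

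Section 11.5.6 says of stopping study drug that "every effort will be made to continue to collect data after" discontinuation. It continues: "Where missing data exist for primary and secondary efficacy endpoints, imputation will occur where specified". Its next paragraph makes multiple imputation the primary method for missing data, with no restriction by reason, and leaves further detail to the SAP.

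For the secondary estimand, data after an intercurrent event are set to missing and "multiple imputed by a MNAR application of SAS Proc MI based on the distribution of data for each treatment arm", using participants without an event. The only sensitivity analysis, in Section 11.5.7, is in the per-protocol set: "Same as primary analysis method. Repeat on primary and secondary estimands with same imputation approach for missing data".

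The SAP's opening statement records that the sponsor terminated the study, that four subjects were randomized, that no primary efficacy data were collected for anyone, and that no efficacy endpoint will be formally analysed.

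**The concern.** Participants who stop for toxicity or lack of efficacy are the least likely to resemble completers, and they are the class for which the primary estimand names no rule. If Section 11.5.6 confines imputation to cases "imputation will occur where specified", their missing scans would stay missing.

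The endpoint offers no cushion. MRI-PDFF is listed at screening (Section 10.2.1) and at Week 24 (Section 10.2.3), and it is absent from the early-termination list in Section 10.2.5. With a single post-baseline scan, the mixed model in Section 11.5.4 has no interim PDFF values to borrow from. A participant without a Week 24 value adds nothing to the treatment contrast unless imputed, although the ITT definition in Section 11.3 requires only randomization and one dose.

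If such participants on active drug lose their benefit, leaving them out makes the drug look better than a treatment-policy estimate should. No planned analysis relaxes the assumption that living participants with missing scans behave like the rest of their arm.

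**Working it through.** **The plan's own figures.** Section 11.11 gives a difference of 3, SD 6, one-sided 5%, 80% power and 15% dropout.

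- Normal approximation: n per arm = 2 × (1.645 + 0.842)² × 6² / 3² = 49.5, so 50.
- Exact t-test (noncentral t): power 79.9% at 50 per arm and 80.6% at 51. The stated 51 per arm, 102 in total, reproduces.
- Dropout: 102 / 0.85 = 120. Reproduces.

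**How many participants could lack a named rule.** Expected missing scans are 0.15 × 120 = 18. The split by reason is not given, so let s be the share stopping for adverse event, lack of efficacy or the other listed reasons, with no scan obtained. Then 18s have no named rule and 120 − 18s are analysed if those are dropped and the rest imputed.

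| s | no named rule | analysed |
|---|---|---|
| 0% | 0 | 120 |
| 25% | 4.5 | 115.5 |
| 50% | 9 | 111 |
| 75% | 13.5 | 106.5 |
| 100% | 18 | 102 |

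The worst case is the planned evaluable number. Planned precision is not at risk, so the question is bias.

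**Size of the bias.** Let a fraction f of the active arm and g of the placebo arm be unscanned discontinuers of this class. Let their true change be less favourable than that of the others in their arm by a and d points. The full-population difference (placebo minus saroglitazar) is the others' difference plus g·d minus f·a. Leaving these participants out therefore overstates the effect by

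bias = f·a − g·d.

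Take a = 3 (active discontinuers revert fully to the placebo mean) and d = 0 (placebo discontinuers resemble placebo completers). The bias is then 3f:

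| f | true difference 3(1 − f) | overstatement 3f | relative to truth |
|---|---|---|---|
| 0% | 3.00 | 0 | 0% |
| 5% | 2.85 | 0.15 | 5% |
| 7.5% | 2.775 | 0.225 | 8% |
| 10% | 2.70 | 0.30 | 11% |
| 15% | 2.55 | 0.45 | 18% |

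The values of f, a and d are all assumptions. If placebo participants who stop for lack of efficacy do worse than placebo completers (d > 0), the bias shrinks. With f = g and a = d it is zero, and with g·d above f·a it runs against the drug.

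**Does the missing rule matter?** A simulation of 2,000 trials used 60 per arm, 9 missing per arm, active-arm dropouts with no drug effect, and ANCOVA on the single post-baseline scan. It assumed a baseline mean of 18, SD 6 and a slope of change on baseline of −0.3; none of these is in the documents. MAR imputation used arm and baseline, with 20 imputations. Mean estimates (saroglitazar minus placebo):

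- all scans obtained: −2.55
- unscanned participants dropped: −3.00
- unscanned participants imputed under MAR: −3.00

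In a single simulated trial the last two differ by 0.08 on average; over trials they agree. Extending the MAR sentence to the unnamed class would complete the wording without moving the expected estimate. The whole 0.45 is the distance between MAR and the placebo-like assumption put into the simulation.

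**Reading the two sections together.** Taken as exhaustive, the sentence in Section 11.5.2.2 would also exclude a scan missed by someone still on treatment, which is the ordinary MAR case. That makes it hard to read as a deliberate restriction. The general sentence in Section 11.5.6 supplies a workable default for the rest.

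**The case for a change.** The strongest reply is that either reading is exposed to the same bias. If dropping and MAR imputation agree, the ambiguity is no comfort. The plan should then set an explicit assumption for these participants, for example imputing them from the placebo arm, or at least add a tipping-point analysis.

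Part of this stands. No analysis probes departures from MAR among living participants, and repeating the same imputation in the per-protocol set does not do so. The MNAR label on the secondary-estimand method is doubtful, because drawing from event-free participants in the same arm is a within-arm completer-like assumption. That source does suit a hypothetical strategy, so the label is at fault and not the method. The references to biopsy and ordinal scores in Section 11.5.6 do not fit an MRI endpoint. Both are clerical.

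Reference-based imputation as the primary method is a debatable choice, though. In the placebo arm it is still MAR from placebo completers. For transplant or bariatric cases it would impute from placebo participants without those procedures, which is not their treatment-policy outcome. That it recovers the truth when dropouts are simulated as placebo-like follows from the set-up and does not show that it is right here.

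The exposure is also narrower than all participants who stop for these reasons: only those without a Week 24 scan are affected. The planned summaries of withdrawal reasons and of adverse events leading to discontinuation would show how many there were and whether the arms differed.

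**Conclusion.** Section 11.5.2.2 leaves a class of missing scans without a named rule, and it sits awkwardly beside Section 11.5.6. This is a gap that an analyst would fill from the general multiple-imputation sentence, and filling it that way leaves the expected estimate unchanged (3.00 against 3.00).

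A bias of 0 to 0.45 points on a difference of 3 requires that 0% to 15% of the active arm stop for these reasons, go unscanned and revert fully to the placebo mean, with no corresponding effect in the placebo arm. The documents supply neither the share nor the behaviour, and the sign could reverse.

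Had the trial run to completion, a sensitivity analysis away from MAR would have been worth having. It did not: Section 11.1 lets the SAP override the protocol, and the SAP presents only safety data because no primary endpoint was collected among the four randomized participants. No estimate, test or conclusion of this trial depends on the rule, so no change is called for.

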#### 11.5.3 Statistical Hypotheses

- o The superiority hypotheses for comparing Saroglitazar Magnesium 4 mg to Placebo are
  - $\circ \quad H_0: \, \mu_p \mu_s \leq 0$
  - $\circ \quad H_1: \mu_p \mu_s > 0$
- $\circ$  Where  $\mu_s$  is the change from baseline to Week 24 in liver fat content for Saroglitazar 4 mg arm and  $\mu_p$  is the change from baseline to Week 24 in liver fat content for placebo arm.

#### 11.5.4 Statistical Methods

Comparison of change from baseline in hepatic fat content between Saroglitazar 4 mg and placebo will be evaluated using mixed models for repeated measures (MMRM) including visit and treatment as factors, baseline value as a covariate and an interaction term treatment x visit. The p-value for the treatment differences (Saroglitazar Magnesium versus Placebo), estimate of LSMEANS treatment difference (Saroglitazar Magnesium – Placebo), and the two-sided 90% confidence interval of the LSMEANS difference will be generated from the MMRM model. Observed values and changes from baseline will be summarized descriptively at each visit for all continuous parameters. The primary endpoint will be analyzed based on the ITT population.

